#### 1.3.2. Minimisation of Risk

Although there are potential risks posed during a cardiac RF ablation procedure, the criteria for subject selection, methods, personnel, facilities, and training that have been specified for this study are intended to minimize the risk to subjects undergoing this procedure.

Robust testing of the investigational devices at component and the system level, within simulated clinical conditions, was successful with no adverse events identified. During the QMODE+ design phase, systematic proactive risk analyses did not identify new hazards and harms. Minimization of Risk has been described per QDOT MICRO™ catheter IFUs within the section Warnings and Precautions for the QDOT MICRO™ Uni-Directional Catheter (M-5276-1043A), which are the same as those listed in the QDOT MICRO™ Bi-Directional IFU (M-5276-1042A) with the exception of the product name. The list of warnings and precautions entail pre-procedural and procedural precautions whereas postprocedural management is in accordance with the ACC/AHA/HRS 2017 Guidelines for the Management of Patients with Atrial Fibrillation. Additionally, the risk of potential adverse events is mitigated by the temperature cutoff setting of the generator and the optimization of the target temperature.

Patient selection: Subjects will be screened carefully prior to enrollment in the study to ensure compliance with the inclusion and exclusion criteria. Both criteria have been developed to reflect the population indicated for commercial use of the QDOT MICRO™ catheter. The exclusion criteria and contraindications have been developed to exclude subjects with a medical history or condition that relates to the contraindications per catheter IFUs and therefore their risk of (unanticipated) adverse events (refer to Section 4.2 for the Exclusion Criteria and the catheter IFUs).

#### Procedure safeguard and post-procedural management:

Investigators skilled in intracardiac mapping and ablation of AF with the use of RF ablation catheters containing contact force technology and qualified training experience with the use of the QDOT MICRO™ system will be selected for participation in the study. AF ablation procedures will be performed in electrophysiology laboratories with the assistance of skilled nurses and technicians. The laboratory will contain sufficient resuscitative equipment and facilities to manage any potential complications. Immediate access to cardiac surgical facilities, as well as a qualified cardiovascular surgeon, will be available during the ablation procedure in the event that surgical intervention becomes necessary.

To proactively manage serious and potentially life-threatening complications during an AF ablation procedure (Atrio-Esophageal Fistula, PV stenosis, Phrenic nerve paralysis and cerebral embolism), the following precautions are highly recommended:

- When ablating near the esophagus (along the posterior wall of the left atrium), take precautions to avoid injuring the esophagus. These may include beginning the ablation with reduced RF power, reducing contact force, reducing application time, increasing the time interval between ablations, esophageal visualization, and/or intraluminal esophageal temperature monitoring.
- When ablating near the phrenic nerve, take precautions to avoid injuring the phrenic nerve, including appropriately reducing RF power, and performing pacing maneuvers to identify the proximity of ablation electrode(s) to the nerve.
- To prevent stenosis of the pulmonary veins, do not place the catheter in the pulmonary veins during the application of RF energy.
- Inspect the saline within the irrigation tubing for air bubbles prior to its use in the procedure. Air bubbles in the irrigation saline may cause emboli.
- To prevent thromboembolism, intravenous heparin (target ACT of ≥325 s) should be administered prior to or immediately following transseptal puncture during AF ablation procedures. The 2017 HRS/EHRA/ECAS/ AOHRS/SOLAECCE expert consensus statement on catheter and surgical ablation of atrial fibrillation recommends systemic anticoagulation with warfarin or a direct thrombin or factor Xa inhibitor for at least 2 months following an AF ablation procedure.

Safety data during enrollment and short follow-up will be routinely monitored by the Medical Safety group.

## 1.3.3. Known Potential Benefits

Current practice guidelines reflect extensive expert reviews of published risks and benefits among various treatment modalities and patient populations. All key published guidelines agree that the primary clinical benefit of catheter ablation for PAF is an improvement in quality of life, following abatement of arrhythmia-related symptoms.

The role of catheter ablation as first-line therapy, prior to a trial of a Class I or III antiarrhythmic agent, has been suggested as an appropriate indication for catheter ablation of AF in patients with symptomatic paroxysmal or persistent AF by the HRS/EHRA/ECAS 2017 Consensus Statement [2]. In this circumstance, the benefits of catheter ablation outweigh the risks (Class IIa); however, the strength of evidence/data supporting this therapeutic modality (Level B) reflects a limited number of clinical studies. Not all expert bodies are in line with the aforementioned expert opinion.

The 2016 ESC-published guidelines and recommendations for the management of AF suggested that in patients who experience symptomatic recurrences of AF despite antiarrhythmic drug therapy, catheter ablation shows better sinus rhythm maintenance with catheter ablation than on antiarrhythmic drugs [49]. However, the guidelines also present that randomized trials showed only modestly improved rhythm outcome with catheter ablation compared to antiarrhythmic drug therapy [49].

Catheter ablation has been used for over two decades to treat AF patients to achieve PVI. Significant catheter design improvements (e.g., irrigated encircling catheters) focus upon improving physicians' abilities to achieve finite entrance block following PVI, reducing damage to neighboring structures and improving procedural efficiency. The QDOT MICRO™ catheter is a steerable multi-electrode luminal catheter with a deflectable tip designed to facilitate electrophysiological mapping of the heart and to transmit radiofrequency (RF) current to the catheter tip electrode for ablation purposes. In addition to force-sensing technology, the catheter incorporates six thermocouple temperature sensors and three micro electrodes embedded in the 3.5 mm tip electrode.

The measured temperature can be used by the operator to assess the efficiency of ablation in real time. The localized temperature measurement will provide a highly sensitive measure of catheter location stability and/or movement during RF application and may reduce the need for additional RF applications.

The micro electrodes will provide high quality localized electrograms that will allow finer endocardial electrical mapping and a better assessment of possible conduction gaps in the ablation lesion sets used to isolate the pulmonary veins and determining bidirectional block of linear lesion sets.

Finally, the catheter tip has incorporated a new angled design of the irrigation ports. This new design allows for reduced incidence/risk of charring and coagulum on the catheter increasing safety during the ablation procedure.

With contact force information and improved temperature feedback in any tip tissue orientation, the QDOT MICRO™ catheter is designed to create durable lesions, in shorter time, with fewer ablation applications, and improved irrigation flow decreasing the opportunity for char and coagulum formation.

The expected benefits of the QDOT MICRO™ System, consisting of a radiofrequency ablation catheter combining microelectrodes, thermocouples, porous tip irrigation and contact force sensing with the nGEN Generator with QMODE+ modality software installed may improve safety and efficiency. There are several types of clinical benefits for catheter ablation that are not specific to the subject device. These catheter ablation clinical benefits include impact of the procedure on clinical management, patient health, and patient satisfaction in the target population.

The QDOT-MICRO™ System may potentially impact the procedure by the following:

- Limit conductive heating and collateral damage to neighboring structures including noncardiac adjacent tissues.
- Increase catheter stability and reduce tissue edema, therefore improve lesion to lesion consistency at very high power for a short duration, since catheter instability in a constantly beating heart and tissue edema remains problematic for the effective lesions using the conventional ablation techniques.
- Contact force sensing capabilities and improved temperature feedback may aid in increasing the effectiveness of RF ablations by maintaining better control for a more effective lesion formation.
- Reduce the procedural time related to ablating the pulmonary vein triggers in the left atrium and improve the PVI efficiency significantly.
- Reduce fluoroscopy exposure for both the patient and the staff.
- Microelectrodes may aid in better assessment of possible conduction gaps in the ablation lesion sets.

 Reduce the amount of fluid loading of the patient as compared to a focal ablation catheter.

# 2. Objectives

The objective of this study is to evaluate the workflow and acute performance of the QDOT MICRO™ catheter used in combination with the nGEN Generator with QDOT software module for the treatment of Patients with Atrial Fibrillation during standard electrophysiology mapping and RF ablation procedures. In this study, QMODE+ will be used as the primary mode for pulmonary vein isolation. If the investigator deems QMODE+ is unable to achieve PVI, the study catheter in QMODE will be used to complete the procedure.

# **3.** Study Design and Endpoints

# 3.1. Description of the Study Design

The QDOT-nGEN study is a prospective, multi-center, non-randomized, interventional clinical workflow study. The study population will consist of up to 50 subjects with minimum of 30 subjects who are scheduled to undergo a clinically indicated ablation procedure for the management of their AF. The study will be conducted at up to 6 centers in Canada.

# 3.2. Study Endpoints

#### 3.2.1. **Primary Endpoint(s)**

The primary endpoint is to confirm pulmonary vein isolation. This is defined as confirmation of entrance block in all targeted PVs after adenosine and/or isoproterenol challenge using the nGEN/ QDOT Micro Ablation System.

#### 3.2.2. Additional Endpoints

The following additional data will be collected and analyzed as part of this study. These data will include but not limited to:

- Adverse events will be collected and evaluated. All events will be reported to the Complaint Handling Unit (CHU).
- Procedural data associated with
  - Catheter ablations outside the PV area
  - $\circ~$  PVI achieved with QMODE+ only among all targeted veins and by subject
  - PVI achieved with combined use of QMODE+ and QMODE among all targeted veins and by subject
  - Need for ablation of acute PV reconnection (touch-up) among all targeted veins and by subject
- Procedural parameters
  - o Total procedure time
  - Mapping time
  - o PV ablation time
  - Total ablation time
  - RF application time
  - o Total Fluoroscopy time
- Total number of RF applications, % QMODE+ applications and % QMODE applications

- Anatomical location of touch-up applications using the QDOT catheter
- Temperature, power, contact force, impedance during RF application
- Confirmation of RF energy delivery from nGEN log files

# 4. Study Population

#### 4.1. Participant Inclusion Criteria

Subjects must meet ALL the following inclusion criteria to be eligible for participation in this study:

- 1. Subjects diagnosed with symptomatic Paroxysmal or Early Persistent\* AF undergoing a catheter ablation procedure through pulmonary vein isolation.
- 2. Age 18 or older.
- 3. Signed the Patient Informed Consent Form (ICF).

\*Definitions for paroxysmal and early persistent AF are based on the 2017 HRS consensus statement.

## 4.2. Participant Exclusion Criteria

Subjects who meet ANY of the following exclusion criteria are not eligible for enrollment.

- 1. If the patient has had a ventriculotomy or atriotomy within the preceding twelve weeks.
- 2. Presence of a myxoma or an intracardiac thrombus.
- 3. Presence of prosthetic valves.
- 4. Presence of active systemic infection
- 5. Patient with an interatrial baffle or patch
- 6. Women who are pregnant (as evidenced by pregnancy test if pre-menopausal), lactating, or who are of child bearing age and plan on becoming pregnant during the course of the clinical investigation.

#### 4.3. Contraindications

The following contraindications are referenced in the IFU for study

- If the patient has had a ventriculotomy or atriotomy within the preceding twelve weeks because the recent surgery may increase the risk of perforation.
- In patients with a myxoma or an intracardiac thrombus as the catheter could precipitate an embolus.
- In patients with prosthetic valves as the catheter may damage the prosthesis.
- In the coronary arterial vasculature due to risk of damage to the coronary arterial vasculature.
- In patients with an active systemic infection because this may increase the risk of cardiac infection.
- Via the transseptal approach in a patient with an interatrial baffle or patch because the opening could persist and produce an iatrogenic atrial shunt.
- Via the retrograde trans-aortic approach in patients who have had aortic valve replacement.
- With a long sheath or short introducer < 8.5 F in order to avoid damage to the catheter shaft.

## 4.4. Participant Withdrawal or Termination

#### 4.4.1. Reasons for Withdrawal or Termination

Participants are free to withdraw from participation in the study at any time upon request without penalty or loss of benefits to which they may otherwise be entitled. Participants will be informed prior to study entry that they are free to withdraw from the study at any time and for any reason without prejudice to their future medical care by a physician or the institution.

An investigator may terminate a subject's participation in the study if:

- Any clinical adverse event (AE), laboratory abnormality, or other medical condition or situation occurs such that continued participation in the study would not be in the best interest of the participant
- Withdrawal is in the subjects' best interest
- The participant no longer meets eligibility criteria or meets an exclusion criterion (either newly developed or not previously recognized) that precludes further study participation.
- Subject withdraws consent
- Subject is lost to follow up

Every subject should be encouraged to remain in the study until they have completed the protocol required 7-day follow-up period.

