Radiofrequency current may cause occlusion of a coronary artery, either by direct thermal damage, spasm, or thrombus formation. Acute coronary artery occlusion is a very rare but potentially life-threatening complication of RFCA [33]. Experience at numerous centers suggests that the risk of coronary occlusion is less than 0.5% [34]. Coronary arterial occlusion could produce myocardial infarction (MI), angina or death. Occlusion of a coronary artery can be treated by restoring coronary blood flow through pharmacological, catheter and/or surgical intervention as medically indicated.

The application of radiofrequency current close to the AV node or His bundle could damage or destroy the normal AV conduction system, producing complete heart block and requiring implantation of a permanent pacemaker.

**Thromboembolic events:** Thrombus generation during the procedure may pose a serious and even life-threatening risk to the patient. Thrombus may form on the ablation electrode during the application of radiofrequency current with or without any change in impedance. The thrombus might become dislodged and embolize to produce an ischemic stroke, MI, or other occlusive injury. Although some observational studies have shown a relatively lower stroke rate after catheter ablation, whether catheter ablation can reduce the thromboembolic risk remains unclear.

The mean incidence of thromboembolism associated with AF ablation was reported by Cappato et al in 2010 to be between 1% and 2% [21]. More recently, Fujii et al have reported incidence of thromboembolism in up to 5% of patients undergoing AF ablation despite perioperative anticoagulation [35]. Ischemic stroke events typically occur within 24 hours of the AF ablation procedure with the higher risk period covering for the first two weeks following ablation [36].

**Pulmonary hemorrhage** is a rare but severe complication of PVI. Late hemoptysis and pulmonary hypertension can occur secondary to pulmonary vein stenosis (PVS) after ablation. Acute pulmonary hemorrhage also has been reported[37]. Mechanical trauma from catheter manipulation is a possible mechanism for pulmonary hemorrhage .

Injury to a cardiac valve may result from catheter manipulation or the application of radiofrequency current (risk <1%)  $[38]^{42}$ . This may produce valvular insufficiency and possibly require valve replacement surgery.

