### 8.4. Early Termination Visit

Subjects may withdraw from the clinical investigation at any time. The decision for the subject to withdraw informed consent must be made independently of influence by the investigator or site personnel. The subject's decision will be documented in the source and eCRF. The investigator may also choose to withdraw a subject from the study if there are safety concerns. If a subject withdraws from the study, the date and reason for withdrawal will be recorded on the appropriate electronic case report form (eCRF).

All data will be collected (as available) until the subject is withdrawn. If the subject is withdrawn due to an adverse event (AE) or serious adverse event (SAE), the investigator should follow the subject until the AE/SAE has resolved or is considered stable. The local CHU will collect the resolution information of any reported SAEs.

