#### **Table 8. Comprehensive List of Anticipated AEs**

Anticipated Adverse Events	
Acute Respiratory Distress Syndrome (ARDS)	Air embolism
Allergic reaction	Allergic reaction to Anesthesia (e.g., hair loss)
Anaphylactic shock	Anemia
Anesthesia reaction	Apnea - sedation induced
Arrhythmia: bradycardia	Arrhythmia: pro-arrhythmias
Arrhythmia: tachycardia	Aspiration pneumonia
Asthmatic attack	Atelectasis
Atelectasis	Atrial fibrillation*
Atrio-Esophageal fistula	Atypical left atrial flutter
AV fistula	Bleeding complications
Bleeding requiring transfusion	Cardiac arrest
Cardiac perforation	Cardiac thrombo-embolism
Cerebro-vascular accident (CVA) / stroke	Chest pain/discomfort
Complete heart block, temporary or permanent	Conduction block: ongoing / resolved

Congestive Heart Failure	Coronary artery dissection
Coronary artery occlusion	Coronary artery spasm
Coronary artery Thrombosis	Damage to the vascular system
Death	Deep venous thrombosis
Diaphragmatic paralysis	Dislodgement of permanent pacing leads
Disseminated Intravascular Coagulation	Dyspnoea
Endocarditis	Epistaxis
Esophageal Injury	Exacerbation of pre-existing
	arrhythmia*
Expressive aphasia	Fainting
Fatigue	Gastric reflux
Gastrointestinal diverticulosis	Gastro-intestinal NOS
Heart Failure	Hematoma (local) /ecchymosis
Hemorrhage	Hemothorax
High / increased creatine phosphokinase	Hypotension
(СРК)	
Нурохіа	Increase in frequency or duration of
	episodes of typical atrial flutter
Increased phosphokinase level	Infection, localized
Infection, systemic	Injury to skin, muscle, connective tissu
	due to body position, electrical
	cardioversion, etc.
Laceration	Leakage of air or blood into the lungs
	or other organs due to perforation
Liver toxicity	Mobile strands in Inferior Vena Cava
Myocardial Infarction	Nausea
Neurological disorders (headache)	Neurological disorders (poor
	coordination)
Neurological disorders (tremor)	Obstruction to the vascular system
Palpitations	Perforation to the vascular system
Pericardial effusion without tamponade	Pericardial effusion resulting in
	tamponade
Peripheral embolus	Pericarditis
Peripheral thromboembolism	Peripheral nerve injury
Phrenic nerve damage	Phlebitis
Pneumothorax	Pleural effusion
Pulmonary edema	Pseudoaneurysm
Pulmonary hypertension	Pulmonary embolism
Pulmonary vein dissection	Pulmonary toxicity, like acute
	pulmonary syndrome
Pulmonary vein thrombus	Pulmonary vein Stenosis
Renal failure	Pump failure
Respiratory failure	Respiratory depression

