### 14.4. Analyses to be conducted

### 14.4.1. General Conventions

Standard descriptive summaries for continuous data include the number of observations with data, mean, standard deviation (SD), median, minimum, and maximum values. The mean and median will be rounded to one decimal place greater than in the raw data where applicable; the standard deviation will be rounded to two decimal places greater than in the raw data where applicable. In cases where this is not applicable (e.g., average time spent), the mean will be rounded to one decimal place; the standard deviation to two decimal places; the minimum and maximum to the nearest whole number. These will be referred to as "continuous summaries" in this document.

For categorical data, the count and percent will be provided. Percentages will be based on the number of subjects without missing data. For adverse event and device effects data, percentages will be based on the number of subjects in the analysis population being used in the analysis. When count data are presented, the percentage for zero counts will be suppressed in order to draw attention to the non-zero counts. Frequency counts will be presented as whole numbers and

percentages will be rounded to one decimal place. This will be referred to as "categorical summaries" in this document.

Adverse events (AE) tables will be sorted by decreasing frequency of events, unless otherwise specified.

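### Investigators may withdraw a treated subject for reasons that can be complications of the ablation, and no rule clearly keeps new adverse events being collected to month 3

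*Combined protocol and SAP*

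**What the plan says.** Section 4.4.1 lists reasons for which the investigator may end a subject's participation. They include an adverse event, the subject's best interest, and this one: "The participant no longer meets eligibility criteria or meets an exclusion criterion (either newly developed or not previously recognized) that precludes further study participation". Section 8.4 adds: "The investigator may also choose to withdraw a subject from the study if there are safety concerns". Neither section limits these reasons to the time before ablation, and safety concerns are not defined.

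Two exclusion criteria in Section 4.2 are relevant here: "Presence of active systemic infection" and "Presence of a myxoma or an intracardiac thrombus". Table 8 lists "Infection, systemic" among the anticipated adverse events. On thrombus, Section 1.3.1 says: "Thrombus generation during the procedure may pose a serious and even life-threatening risk to the patient".

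On what happens to the data, Section 8.4 says: "All data will be collected (as available) until the subject is withdrawn". Sections 4.4.2 and 8.4 keep a subject withdrawn because of an adverse event under follow-up until that event resolves or is stable. Sections 9.3 and 9.4.1 require recorded events to be followed to resolution. Section 4.4.1 asks sites to encourage subjects to stay through the 7-day follow-up, whereas Section 8.3 requires follow-up through 3 months (days 76 to 104).

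For the analysis of adverse events, Section 14.4.1 says that "percentages will be based on the number of subjects in the analysis population being used in the analysis". Section 14.4.7 imputes nothing.

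**The concern.** After the index procedure, taking part in the study means answering two contacts, either of which may be remote. Ending participation at that stage removes no study exposure; it only ends observation. If the reason for ending it can be a complication of the ablation, the loss of later safety data depends on the safety outcome.

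The effect runs in one direction. A withdrawn subject stays in the Safety Analysis Set denominator, and any later event that nobody recorded is counted as absent. The protocol describes risks that extend past the day 7 contact: Section 1.3.1 puts the higher-risk period for ischemic stroke at the first two weeks, and describes late hemoptysis secondary to pulmonary vein stenosis and fistula linked to delayed diagnosis of esophageal perforation. Up to six centers would each apply undefined discretion. What is at stake is the descriptive 3-month safety summary.

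**Working it through.** The plan gives no figure to reproduce. The size of 30 to 50 subjects (Section 14.3) has no hypothesis, power or dropout input. The check is a comparison of texts, followed by simple arithmetic on assumed numbers of early leavers.

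**1. Which exclusion criteria can arise from the ablation?**
- Active systemic infection (exclusion 4): yes. Systemic infection, sepsis and endocarditis are in Table 8.
- Intracardiac thrombus (exclusion 2): yes. Thrombus generation is a named procedural risk in Section 1.3.1.
- Prosthetic valve (exclusion 3): rarely and indirectly. Section 1.3.1 gives valve injury as below 1%, with replacement only a possibility.

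**2. What continues and what stops after the investigator withdraws a treated subject?**
- The event behind the withdrawal: followed until resolved or stable (4.4.2, 8.4).
- Other events already recorded: followed to resolution however the withdrawal is coded (9.3, 9.4.1).
- New events between withdrawal and month 3: no specific rule collects them, and Section 8.4 ends data collection at withdrawal. Section 19 does continue follow-up of enrolled subjects, but only when the whole study is stopped early for safety.

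**3. Weight of one missed subject.** Shortfall in a by-subject rate = m/N, where m is the number of withdrawn subjects, each with one unseen later event that would have counted. The protocol does not give m; 1 to 3 is an assumption.

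| m | N=30 | N=50 |
|---|---|---|
| 1 | 1/30 = 3.3 points | 1/50 = 2.0 points |
| 2 | 2/30 = 6.7 points | 2/50 = 4.0 points |
| 3 | 3/30 = 10.0 points | 3/50 = 6.0 points |

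These are maxima, because they assume that every leaver has a later event. Example for one event term with exact (Clopper-Pearson) 95% limits: 1/30 observed is 3.3% (0.1 to 17.2); with three unseen events it would be 4/30 = 13.3% (3.8 to 30.7). At N=50 the pair is 2.0% (0.1 to 10.6) and 4/50 = 8.0% (2.2 to 19.2).

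**4. Which summary rows can move?** Section 14.4.6 counts a subject once per by-subject summary. Suppose 2 of 30 subjects are withdrawn after a complication, each has a later unseen serious event of the same term, and nobody else has an event.
- Any adverse event: 2/30 = 6.7% either way.
- Any serious event: 2/30 either way if the first events were serious; 0/30 instead of 2/30 only if both were non-serious.
- The specific later term: 0/30 instead of 2/30.
- By-event count: 2 instead of 4.

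**5. How many subjects could this concern?** Expected number = N × rate, with the rates in Section 1.3.1.
- Infection, local or systemic, below 0.5%: fewer than 30 × 0.005 = 0.15 or 50 × 0.005 = 0.25 subjects.
- Valve injury, below 1%: fewer than 0.3 or 0.5 subjects.
- Major complications, 0.8% to 5%: 0.24 to 1.5 subjects at N=30 and 0.4 to 2.5 at N=50. The chance of at least one, 1 − (1 − p)^N, is 21% to 79% at N=30 and 33% to 92% at N=50.

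These count subjects with a complication. Only some would be withdrawn, and only some of those would have a new event. The protocol gives no rate for intracardiac thrombus and schedules thrombus imaging only before ablation.

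**6. Follow-up lost.** Taking month 3 as day 90, the centre of days 76 to 104, a subject who leaves after day 7 loses 90 − 7 = 83 days, or 83/90 = 92% of the planned period.

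**The case against.** The wording is permissive, and the exclusion-criterion reason applies only where the criterion precludes further participation. An infection or a new valve hardly precludes a telephone call, so a sensible investigator would keep such subjects. Section 5.1 asks investigators to follow subjects to the end of the protocol, and Section 9.4.1 makes them responsible for events through the end of the study. Any loss would be visible: the date and reason for withdrawal are recorded (4.4.2), discontinuations are tabulated by primary reason (14.4.2), and adverse events leading to discontinuation are a reported category (14.4.6). The study is descriptive and its primary endpoint is acute.

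Most of this is fair and limits the point, but it does not close the gap. The general duties in 5.1 and 9.4.1 do not say that they survive withdrawal, while Section 8.4 speaks to that case and ends data collection. The tables would show that someone left; they would not recover what happened next.

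Stronger readings are tempting, and the documents do not support them:
- A reader might infer that the complication itself is lost, or that a withdrawal coded as an exclusion criterion has no follow-up at all. Sections 9.3 and 9.4.1 follow every recorded event whatever the coding.
- A reader might infer that two such withdrawals in 30 would turn 6.7% into 0% for serious events generally. Under Section 14.4.6 that holds only if the first events were non-serious, or for a specific later term.
- A reader might add atriotomy to the overlapping criteria. Section 1.3.1 mentions surgical repair after perforation, not atriotomy.
- A reader might conclude that investigator discretion should be removed after treatment. The best-interest provision protects subjects and can stay; only data collection needs to be separated from it.

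**Conclusion.** The point holds in a limited form. After the single ablation, Sections 4.4.1 and 8.4 allow withdrawal for reasons that include at least two possible results of the ablation, and no text clearly keeps the subject in collection of new adverse events to month 3. The 7-day retention sentence in 4.4.1 also sits below the 3-month requirement in 8.3. With a full-set denominator and no imputation, any bias is toward a better safety profile.

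For a specific later event term, or for any serious event when the first was non-serious, the size is 3.3 points per missed subject at n=30 and 2.0 at n=50. This assumes that the subject was withdrawn before a later event that then went unrecorded. The number of such subjects is an assumption and, on the protocol's own complication rates, is likely to be small. The any-adverse-event row barely changes, because the triggering event is already counted. The acute primary endpoint is not affected. This is a cheap improvement to the 3-month safety summary, not a threat to the study's main result.

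**What to change.** Amend Sections 4.4.1 and 8.4 to say two things. First, after study catheter insertion, a newly met exclusion criterion is recorded and does not by itself end safety follow-up. Second, when the investigator withdraws a treated subject for any reason, adverse event collection continues through the day 7 and month 3 contacts, remotely if need be, unless the subject withdraws consent, dies or is lost to follow-up. Keep the investigator's best-interest discretion as it is. Reconcile the 7-day retention sentence in 4.4.1 with the 3-month follow-up in 8.3.

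The cost is a few sentences in an amendment. The contacts are already scheduled and may be made by telephone or telehealth, and no treatment or clinical care changes. The downside is that sites keep contacting a few subjects whom they might otherwise have dropped.
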